10.1.2 Surveillance period for adverse events

All adverse events occurring within 30 days following administration of each study immunization will be recorded irrespective of severity or whether or not they are considered vaccination-related.

Solicited adverse events will be elicited for a 7-day surveillance period (day of vaccination and study days 1, 2, 3 and 7 and unsolicited adverse events will be recorded during a 30-day surveillance period. Serious adverse events will be recorded throughout the study.

Instances of death, cancer or congenital abnormality in offspring of a study subject if brought to the attention of the investigator at any time after cessation of study AND suspected by the investigator to be related to study vaccine, will be reported to the sponsors and GSK Biologicals.

10.1.3 Recording adverse events

At each visit/assessment, the investigator will evaluate all adverse events observed by the investigators or reported by the participant. New adverse events will be recorded in the Adverse Event form within the participant's CRF. Solicited and unsolicited adverse events will be recorded on separate pages of the CRF. The nature of each event, date and time (where appropriate) of onset, outcome, intensity and relationship to vaccination will be established. Any corrective treatment will be recorded in the CRF. As a consistent method of soliciting adverse events, the participant will be asked a non-leading question such as: "Have you felt different in any way since receiving the vaccine or since the last visit?" The investigator will record only those adverse events having occurred within the time frames defined above.

Adverse events already documented in the CRF, *i.e.* at a previous assessment and designated as 'ongoing' will be reviewed at subsequent visits, as necessary. If these have resolved, the documentation in the CRF will be completed, including the date that the adverse event resolved. If an adverse event changes in frequency or intensity during a study period, a new record of the event will be started.

10.1.4 Solicited adverse events

Local (injection site) adverse events	General adverse events
Pain at injection site	Fever (oral body temperature \geq 37.5°C)
Swelling at injection site	Chills
Erythema	Nausea
Limitation of arm motion (abduction of	Headache
shoulder)	Malaise
	Myalgia

Joint pain

Oral temperature will be recorded at the time of the clinic visit. If additional temperature measurements are recorded at another time of the day, the highest temperature will be recorded.

The assessment of severity/intensity will be as described in Section 10.2. For general signs and symptoms reported, the investigators will assign causality as described in Section 10.3 For all signs and symptoms reported, the investigators will report the outcome as described in Section 10.5.2.

10.1.5 Unsolicited adverse events

Unsolicited adverse events will be recorded in the CRF. Unsolicited adverse events are adverse events reported by the participants that are different from those solicited symptoms defined in the preceding section and/or that begin after the 7-day surveillance period for solicited adverse events.

10.2 Assessment of intensity of non-serious adverse events

For each solicited symptom the participants will be asked if they sought medical advice for this symptom. For all other adverse events than those in Table 5, maximum intensity will be assigned to one of the following categories:

0 = No adverse event

1 = An adverse event which is easily tolerated by the subject, causing minimal discomfort and not interfering with everyday activities.

2 = An adverse event that is sufficiently discomforting to interfere with normal everyday activities.

3 = An adverse event that prevents normal, everyday activities. Such an adverse event would for example prevent attendance at work/school and would require the administration of corrective therapy.

Intensity of the following adverse events will be assessed as described in Table 5:

Table 5: Assessment of adverse event intensity

Version 17,	DEAP/MRTC/MMVDU	-
00	NUT IN TAUTIAT	

Adverse Event	Intensity grade	Intensity definition			
Pain at injection site	0	None			
jere en	1	Pain that is easily tolerated			
	2	Pain that interferes with daily activity			
	3	Pain that prevents daily activity			
Swelling at injection site	0	0 mm			
Record size	1	$>0 - \le 20 \text{ mm}$			
	2	>20 - ≤ 50 mm			
	3	>50 mm			
Erythema at injection site	0	0 mm			
Record size	1	$>0 - \le 20 \text{ mm}$			
	2	>20 - ≤ 50 mm			
	3	>50 mm			
Limitation of arm motion -	0	None			
Abduction at the shoulder	1	>90° but <120°			
	2	>30° but <90°			
	3	<30°			
Fever	0	<37.5°C			
Record oral temperature	1	37.5 - ≤38.0°C			
-	2	>38.0 - ≤39°C			
	3	>39°C			
Chills	0	None			
	1	Chills that are easily tolerated			
	2	Chills that interfere with daily activity			
	3	Chills that prevent daily activity			
Nausea	0	None			
	1	Nausea that is easily tolerated			
	2	Nausea that interferes with daily activity			
	3	Nausea that prevents daily activity			
Headache	0	None			
	1	Headache that is easily tolerated			
	2	Headache that interferes with daily activity			
	3	Headache that prevents daily activity			
Malaise	0	None			
	1	Malaise that is easily tolerated			
	2	Malaise that interferes with daily activity			
	3	Malaise that prevents daily activity			
Myalgia	0	None			
	1	Myalgia that is easily tolerated			
	2	Myalgia that interferes with daily activity			
	3	Myalgia that prevents daily activity			
Joint pain	0	None			
	1	Joint pain that is easily tolerated			
	2	int pain that interferes with daily activity			
	3	Joint pain that prevents daily activity			

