6 STUDY DESIGN AND METHODOLOGY

6.1 Overview

- Double blind, randomized controlled dose escalation phase I study
- One study center
- Screening will be done within 35 days prior to the first immunization
- Dose escalating by approximately 25µg and 50µg of FMP2.1 adjuvanted with 0.25 mL and 0.5 mL of AS02A, respectively
- At each of the two FMP2.1 dose levels, 30 adults will be randomized to receive either FMP2.1/AS02A (n=20) or RabAvert® vaccine (n=10)
- Immunization schedule will be on study days 0, 30 + 7, and 60 + 7
- Each consecutive immunization with the 50 µg dose of FMP2.1 will be administered at least 14 days after the corresponding immunization with the 25 µg dose of FMP2.1 to permit review of day 7 safety laboratory results
- Route of immunization will be the deltoid muscle IM
- CRFs will serve as source documents. Only information that cannot be collected initially onto CRFs (namely, clinical laboratory test results and adverse event medical records) will first be collected onto separate source documents prior to transcription into CRFs.
- Study duration will be approximately 12 months per participant
- 7-day surveillance (day of vaccination and study days 1, 2, 3 and 7 for solicited adverse events
- 30-day surveillance for unsolicited adverse events
- Follow-up of serious adverse events (SAEs) until resolution
- Beginning Study Day 120, participants will be visited and assessed by local guides at home at monthly intervals and will be asked to return to clinic every 3 months for safety surveillance.
- The primary analysis will be conducted for all primary and secondary endpoints at a datalock-point one month post Immunization 3 (study day 90), after which the Primary Study Report will be produced.
- The study will then continue in a single-blind fashion. Data gathered during this period will be reported in an addendum report.
- At the end of the study participants will be informed which vaccine they received and those who received malaria vaccine will be offered immunization with the rabies vaccine.

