6.2.1 Determination of local clinical laboratory test reference ranges

In most African countries, reference ranges for clinical laboratory tests are those used in clinical laboratories from Europe and the United States. Laboratory tests such as hemoglobin concentration, white blood cell count, platelet count, serum creatinine and liver enzymes concentration, which are used to determine malaria vaccine potential toxicity, have a different distributions in the West African populations than in European and American populations (61). A survey was therefore undertaken in Bandiagara in March 2003, to determine local reference intervals for clinical laboratory values. This survey followed the methods described in the National Committee for Clinical Laboratory approved guidelines (NCCLS) (62). 120 each healthy male and female residing in Bandiagara were included and reference limits were calculated nonparametrically by taking the 2.5 and 97.5 percentiles of the observed sample values. The 95% confidence intervals of the reference limits were also calculated. The reference intervals calculated were used to establish the upper limits of normal ranges to determine locally appropriate exclusion criteria and toxicity ranges for adverse events for this trial.

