10.1 Eliciting and documenting adverse events

10.1.1 Adverse event definition

An adverse event includes any noxious, pathological or unintended change in anatomical, physiological or metabolic functions as indicated by physical signs, symptoms and/or laboratory detected changes occurring in any phase of the clinical study whether associated with the study vaccine or active comparator vaccine and whether or not considered vaccination related. This includes an exacerbation of pre-existing conditions or events, intercurrent illnesses, or vaccine or drug interaction. Symptomatic uncomplicated or severe malaria infection will be coded as adverse events as will any other acute illness, throughout the 12 months of the study. Anticipated day-to-day fluctuations of pre-existing conditions that do not represent a clinically significant exacerbation need not be considered adverse events. Discrete episodes of chronic conditions occurring during a study period will be reported as adverse events in order to assess changes in frequency or severity.

Adverse events will be documented in terms of a medical diagnosis. When this is not possible, the adverse event will be documented in terms of signs and/or symptoms observed by the investigator or reported by the subject at each study visit. Pre-existing conditions or signs

Page 51 of 96 Version 17, DEAP/MRTC/MMVDU CONFIDENTIAL

and/or symptoms (including any which are not recognized at study entry but are recognized during the study period) present in a participant prior to the start of the study will be recorded on the participant's CRF. Any hospitalization will be considered a serious adverse event. Adverse events to be recorded as endpoints are described in Section 10.1.4. All other adverse events will be recorded as unsolicited adverse events.

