15.4 Safety Monitoring Committee (SMC)

An independent Safety Monitoring Committee will be constituted to help the Medical Monitor review safety data in real time. This committee will consist of the Local Medical Monitor and at least 2 other independent experts, one an experienced senior Malian physician, and the other an expert on conducting and/or monitoring clinical trials. The role of the SMC will be to provide safety oversight over the conduct of the trial. It will review safety data between immunizations and advise on progression to the next immunization. The Safety Monitoring Committee will hold three conference calls to review the safety data generated from the trial up to that point. Each will occur approximately two to three weeks after each immunization with the 25 µg dose level. The purpose of these conference calls will be to review the accumulated safety data in order to advise whether or not the study can proceed to the subsequent immunization with the 50 µg dose level specifically, and whether the trial can proceed generally. The study will not proceed to the next immunization unless explicitly agreed to by a majority of the members of the Safety Monitoring Committee, either in the form of a letter, fax or email from the SMC chair. In the event that the SMC identifies a safety concern, the collaborative group including the investigators, DMID, WRAIR and GSK will review all safety data in order to decide whether to give the next sequential dose. Senior investigators and representatives from DMID, WRAIR, GSK and USAMMDA will be invited to but not obligated to participate in the conference calls during open sessions, which will be followed by closed sessions including only SMC members.

The investigator will inform the SMC of:

- All subsequent protocol amendments, informed screening or study consent form changes or revisions of other documents originally submitted for review
- Serious adverse events (SAEs) and grade 3 adverse experiences (as defined in Table 5, section 10.2) occurring during the study, regardless of relationship to the study vaccine
- New information that may affect adversely the safety of the subjects or the conduct of the study.

Page 66 of 96 Version 17, DEAP/MRTC/MMVDU CONFIDENTIAL

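### Section 10.2 grades laboratory adverse events on a daily-activity scale, and the event-driven SMC notice in Section 15.4 has no laboratory trigger

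*Combined protocol and SAP*

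**What the plan says.** Section 10.1.1 includes in the definition of an adverse event "physical signs, symptoms and/or laboratory detected changes occurring in any phase of the clinical study".

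Section 10.2 then sets two scales for non-serious events. Table 5 grades the solicited items one by one. For the rest: "For all other adverse events than those in Table 5, maximum intensity will be assigned to one of the following categories". Grade 1 of that general scale reads "An adverse event which is easily tolerated by the subject, causing minimal discomfort and not interfering with everyday activities". Grade 2 requires interference with normal activities, and grade 3 requires that they be prevented.

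Section 15.4 lists what the investigator must report to the SMC. The item on events is "Serious adverse events (SAEs) and grade 3 adverse experiences (as defined in Table 5, section 10.2) occurring during the study", whatever the relationship to vaccine. New information bearing on safety is a separate item.

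Section 6.2.1 says the local reference survey was used to set "locally appropriate exclusion criteria and toxicity ranges for adverse events for this trial". Section 6.4 prints the exclusion limits. The protocol prints no laboratory grade cut-offs, and Sections 10.2 and 15.4 do not refer to the ranges.

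Section 6.1 explains the gap of at least 14 days between the two dose levels: it is there "to permit review of day 7 safety laboratory results".

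**The concern.** Laboratory toxicity is often silent. A scale built on how the participant feels cannot tell a trivial symptom-free change in ALT, creatinine or platelets from a large one. The plan does not merely leave laboratory grading open. Its catch-all sentence assigns these events to a scale that gives the same answer at every size.

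Safety is the primary objective, and the stagger between dose levels is justified by laboratory review. The protocol's own background section (4.3.7) describes elevated ALT reported as a serious event in earlier adult work with this adjuvant: one case in a vaccine recipient and four in rabies-vaccine controls. A silent laboratory finding is therefore something the plan should be able to grade and pass on by rule.

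**Working it through.** No design figure depends on this point, so the check is mainly a reading of the rules together.

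**1. What Table 5 covers.** Pain, swelling, erythema, limitation of arm motion, fever, chills, nausea, headache, malaise, myalgia and joint pain: 11 items, all solicited, none from the laboratory.

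**2. Grade and notice by type of non-serious event.** The reference in 15.4 can be read narrowly (Table 5 only) or broadly (any grade 3 defined in Section 10.2).

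| Non-serious event | Scale | Can reach grade 3? | Notice, narrow reading | Notice, broad reading |
|---|---|---|---|---|
| Solicited item | Table 5 | Yes | Yes | Yes |
| Unsolicited event that prevents activity | General | Yes | No | Yes |
| Symptom-free laboratory abnormality | General | No | No | No |

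The broad reading rescues unsolicited events. It does not help the laboratory row, because grade 3 on the general scale still requires prevented activity. As an illustration, take an ALT of ten times the exclusion limit of 43 IU/L: 10 × 43 = 430 IU/L. If it is symptom-free and judged non-serious, it is grade 1 and triggers no notice under either reading.

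**3. A related mismatch.** Section 10.1.1 sends every event that is not solicited to the unsolicited category, while 10.1.5 describes that category as events the participants report. A laboratory finding does not fit that description.

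**4. Other routes to the SMC.**
- Serious events, including important medical events (10.5.1), go to the SMC within 24 hours (10.5.2). Someone must first judge the finding serious.
- New safety information (15.4) also depends on judgement.
- The Local Medical Monitor sits on the SMC and passes on relevant safety information (15.3, 15.4), again by judgement.
- Scheduled review (6.1, 7.1.5, 15.4) looks at accumulated data and is not filtered by grade. There are three calls, each about two to three weeks after a 25 µg immunization and before the corresponding 50 µg immunization. The third therefore precedes the third 50 µg dose, and none is scheduled after it. What remains is the SMC review of safety concerns before unblinding (9.4.2).

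**5. Size of the window without a scheduled call.** Panels (CBC, creatinine, ALT) after the third dose, per participant:
- by the visit descriptions in 7.1.6: Days 67 and 90 plus Visits 21 to 23, so 1 + 1 + 3 = 5;
- by Table 3 and Section 8.1, which add Day 74: 6.

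For the 20 recipients of 50 µg: 5 × 20 = 100 to 6 × 20 = 120 panels. This counts the planned panels to which the gap applies. It does not predict how many will be abnormal.

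**6. Link to Table 6.** The plan's one design calculation is Pr(at least one event in 20) = 1 − (1 − p)^20. At 1%, 5%, 8% and 10% this gives 0.182, 0.642, 0.811 and 0.878, matching the printed 0.18, 0.64, 0.81 and 0.88. These figures take it that every event is recognised. If only a share s of severe events is recognised as severe (an assumption; the documents give no value), p becomes p × s. At p = 8%:

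| s | 100% | 75% | 50% | 25% |
|---|---|---|---|---|
| Pr(at least one recognised in 20) | 0.81 | 0.71 | 0.56 | 0.33 |

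Table 6 itself is correct.

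**The case against.** A reader might infer that the SMC hears only of grade 3 items in Table 5, so that a severe silent toxicity would go unseen. The documents do not support that. The SMC also receives all serious events and new safety information, may ask for more information, and must agree by majority before the next immunization. Day 7 results from each 25 µg immunization are available for review before the matching 50 µg immunization, whatever grade was recorded. The background section shows that raised ALT has been classed as serious before, and Section 10.2 governs non-serious events only.

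A reader might also infer that laboratory analysis is confined to values thought clinically relevant, or that the primary endpoint tables would understate laboratory toxicity. Neither follows. Section 12.5.3 also compares hemoglobin, creatinine and ALT levels over 12 months. Section 12.1 defines the primary endpoints as solicited symptoms, unsolicited symptoms and serious events, and laboratory parameters have their own heading in 12.5.3. Section 10.4 follows clinically significant abnormalities to resolution or explanation at any grade.

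All of that stands, and it limits the point. It does not remove it. Three of the four routes depend on someone recognising the finding without a stated threshold. The scheduled review has no laboratory criterion and ends before the third 50 µg dose. The level comparisons leave out platelets and white cells and do not show which participants had a severe value.

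**Conclusion.** The point holds in limited form. By the stated rule, a symptom-free laboratory abnormality judged non-serious is grade 1 at any size, and the event-driven SMC notice has no laboratory trigger. Read literally, that notice also excludes unsolicited grade 3 events, though its wording is ambiguous there. The toxicity ranges may exist outside the protocol; the defect is that no grading or notice rule uses them.

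It would be wrong to conclude that such an event could not reach the SMC or that escalation review is blind to laboratory results. The exposure is to findings that are severe, silent and not judged serious. It is greatest after the third 50 µg dose, where 100 to 120 panels in 20 recipients fall after the last scheduled call. That conclusion assumes the general scale is applied as written and that no separate document overrides it. The number of events affected cannot be estimated from the documents.

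**What to change.** Reconcile Sections 6.2.1, 10.1.1, 10.2 and 15.4:

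- In 10.2, add a laboratory grading table based on the site toxicity ranges named in 6.2.1, and take laboratory events off the activity scale.
- In 15.4, reword the notice to cover grade 3 events on any 10.2 scale: solicited, unsolicited or laboratory.
- In 12.5.3, add the worst post-dose laboratory grade by group to the level comparisons already planned.

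The cut-offs are for the sponsor to set; none is proposed here. The cost is one table, some wording and slightly more SMC notices, with no added visits or blood draws.

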10.3 Assessment of causality

Every effort will be made by the investigator to explain each adverse event and assess its causal relationship, if any, to administration of the study vaccine(s).

The degree of certainty with which an adverse event can be attributed to administration of the study vaccine(s) (or alternative causes, e.g., natural history of the underlying diseases, concomitant therapy, etc.) will be determined by how well the event can be understood in terms of one or more of the following:

- Reaction of similar nature having previously been observed with this type of vaccine and/or formulation.
- The event having often been reported in literature for similar types of vaccines.
- The event being temporally associated with vaccination or reproduced on re-vaccination.

All solicited local (injection site) reactions will be considered causally related to vaccination. The investigators will assess the causality of all other adverse events using the following method:

In your opinion, did the vaccine(s) possibly contribute to the adverse event?

- NO : The adverse event is not causally related to administration of the study vaccine(s). There are other, more likely causes and administration of the study vaccine(s) is not suspected to have contributed to the adverse event.
- YES : There is a reasonable possibility that the vaccine contributed to the adverse event.

If an AE is determined not to be causally related to administration of a study vaccine, the investigators will specify the likely cause if one can be determined.

10.4 Following-up of adverse events and assessment of outcome

Investigators will follow up subjects with serious adverse events until the event has resolved or until the condition has stabilized regardless of when this occurred in relation to the study conclusion. Investigators will follow up participants with non-serious adverse events until the participant completes the study. Clinically significant laboratory abnormalities, as well as any adverse event, will be followed up until they have returned to normal, or until a satisfactory explanation has been provided. Reports relative to the subsequent course of an adverse event noted for any subject will be submitted to the Study Monitor.

Outcome will be assessed as:

- 1 = Recovered
- 2 = Recovered with sequelae
- 3 = Ongoing at participant study conclusion
- 4 =Died
- 5 = Unknown

